If the request occurs between scheduled visits or at a scheduled telephone visit then the subject will require a Retreatment Assessment Visit prior to receiving study retreatment (some retreatment criteria can be assessed prior to the Retreatment Assessment Visit).

If the request occurs at a scheduled visit then the Retreatment Assessment Visit procedures should be performed at the same visit.

Retreatment criteria

The retreatment criteria are as follows:

- 1) Retreatment requested by subject;
- 2) More than 12 weeks (84 days) since the previous IMP administration;
- 3) CCI [REDACTED]

- 5) In the investigator's opinion it is safe and appropriate to provide a retreatment.

Retreatment should ideally occur within 14 days of confirmation of eligibility for retreatment and can occur up to and including Week 104 following the first IMP administration.

Retreatment follow-up

Follow-up after each retreatment follows the same schedule as the first IMP administration:

- Week 1 (Day 8) (telephone)
- Week 2 (Day 15) (clinic visit)
- Week 4 (Day 29) (telephone)
- Week 6 (Day 43) (clinic visit)
- Week 12 (Day 85) (clinic visit)
- Every 12 weeks (telephone visits; until retreatment received or EOS at Week 104 116).

Details of the procedures performed at each Retreatment Follow-up Visit are contained in [Table 3](#).

End of Study Visit

The EOS Visit will take place between 104 and 116 weeks after the first IMP administration (Day 1). Subjects may receive study retreatment up to and including Week 104 and a minimum of 12 weeks of follow-up is required after each IMP administration. For those subjects completing the study, the EOS Visit will occur:

- 104 weeks after the first IMP administration; if it has been more than 12 weeks since the previous IMP administration
- At the Week 12 Retreatment Follow-up Visit, if the subject received their most recent IMP administration between Week 92 and Week 104 following their first IMP administration.

Early discontinuation

A subject who discontinues early should, if at all possible, be followed-up for at least 12 weeks following their most recent IMP administration and should attend the EOS Visit.

Number of subjects planned: 330 randomised subjects.

Diagnosis and criteria for inclusion:***Inclusion criteria***

The following inclusion criteria will be assessed at the beginning of the Screening process:

- 1) Written informed consent prior to any study-related procedure.

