7 STATISTICAL METHODS

7.1 General Principles

All data processing, summarisation and analyses will be performed using the SAS Environment / Version 9.4 (or later) of the SAS® statistical software package.

All data collected during the study will be presented in listings without any imputation by treatment group, subject, assessment and visit (where applicable), unless otherwise specified.

Data will be presented in summary tables by treatment group (as described below), assessment and visit (where applicable).

Overall, the analysis strategy is to evaluate efficacy and safety data from the initial DBPC Cycle and to evaluate efficacy and safety over repeated Dysport treatments, using analyses by Dysport Cycle (Dysport Cycle 1, 2...etc.), as illustrated in schematic diagram later in this section. In general, tables associated with the DBPC Cycle will be separate from the tables assessing repeat treatment with Dysport which are presented by Dysport Cycle:

- During analysis of the DBPC (DBPC cycle), data will be displayed using the following treatment group labels, in the order presented:
 - Placebo
 - Dysport 600 U
 - Dysport 800 U
 - All Dysport
- During analysis by Dysport Cycle, data will be displayed by number of Dysport treatments (see diagram below) using the following treatment group labels:
 - Dysport Cycle 1
 - Dysport 600U
 - Dysport 800U
 - All Dysport
 - Dysport Cycle 2
 - Dysport 600U
 - Dysport 800U
 - All Dysport
 - Dysport Cycle X

Statistical Analysis Plan

Version: Final v2.0
September-2018
Ipsen Protocol No. D-FR-52120-222
000000146259

[figure not shown]
Date of Issue: 21-
Covance Study ID:

- Dysport 600U
- Dysport 800U
- All Dysport

Analysis of Dysport Cycle 1 will therefore include (see diagram below):

- Data from subjects who received a Dysport treatment after having initially received placebo as their first study treatment on Day 1 i.e. will only use data from their first Dysport treatment,
- Data from subjects who received Dysport as their first study treatment on Day 1

Schematic diagram summarising concept of Dysport Cycles:

Descriptive summary statistics for continuous variables will include the number of subjects (n), mean, standard deviation (SD), median, minimum and maximum.

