7.7.1 Adverse Events

All AEs will be coded by Sponsor using MedDRA v21.0 (March 2018); (the latest version if updated during the study), and will be classified by MedDRA preferred term and system organ class.

A TEAE is defined as any AE with start date/and time at or after the date/and time of the first dose of IMP, or any AE with start date/and time prior to the date/and time of the first dose of IMP whose intensity worsens at or after the date/time of the first dose of IMP. The Pre-treatment AE is defined as any AE with start date/and time prior to the first dose of IMP administration in DBPC Cycle, and after the date of informed consent.

All TEAEs will be assigned to either DBPC Cycle and/or Dysport Cycle X based on the start date and time, or intensity increase date. For example, for presentation of TEAEs by Dysport Cycle, if the start time/intensity increase time of TEAE is at or after the time of treatment administration of Dysport Cycle X, Day 1 and prior to the time of treatment administration of Dysport Cycle X+1, Day 1, the TEAEs will be assigned to Dysport Cycle X.

In this study, an AESI is for Dysport is TEAEs that suggest a possible remote spread of effect of the toxin or events suggestive of hypersensitivity like reactions. TEAEs due to possible remote spread of the effects of Dysport will be identified using the list of MedDRA PTs compatible with the mechanism of action of BTX-A and based on the recommendations from the Committee for Medicinal Products for Human Use (CHMP) and the Food and Drug Administration (FDA). TEAEs potentially representing hypersensitivity reactions will be identified using the Standardised MedDRA Query (SMQ) (narrow search query) for hypersensitivity reactions. A list of MedDRA preferred terms, used to identify any potential AESI, is provided in Appendix VI.

Statistical Analysis Plan

Version: Final v2.0

September-2018

Ipsen Protocol No. D-FR-52120-222

000000146259

Date of Issue: 21-

Covance Study ID:

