- any UTI TEAEs
 - UTI TEAEs leading to withdrawal
 - serious UTI TEAEs
- TEAE leading to death

In view of the anticipated difference in duration of the Dysport and placebo treatment cycles, this overview table will also be provided including only TEAEs occurring any time after first dose of IMP until up to 12 weeks after first IMP treatment administration.

A similar overview table will be produced for the number and percentage of subjects with at least one of the following events occurred pre-treatment for randomised subjects. The number of occurrences of the following events will be presented as well.

- any AE
 - Intensity of AE (mild, moderate, severe)
- any SAE
 - any SAEs leading to withdrawal
- AE leading to death

TEAEs will be summarised overall, for DPBC cycle, and Dysport Cycles with the number and percentage of subjects with TEAEs presented by primary SOC and PT. In addition, this table will be provided including only TEAEs occurring up to 12 weeks after first IMP treatment administration. This will also be summarised by aetiology of NDO.

The same summaries for overall, for DBPC Cycle, and Dysport Cycles with the number and percentage of subjects with TEAEs presented by primary SOC and PT will be presented for serious TEAEs, IMP-related TEAEs, TEAEs leading to withdrawal, TEAEs of special interest, and other protocol defined TEAEs. TEAEs with PTs observed in $\geq 1\%$, $\geq 2\%$, and $\geq 5\%$ of subjects and IMP-related TEAEs with PTs observed in $\geq 1\%$, $\geq 2\%$, and $\geq 5\%$ of subjects will be summarised as well.

Additionally, TEAEs will be tabulated by decreasing overall PT frequency and intensity in each SOC and PT category.

The above will also be presented for SAEs.

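### The 12-week adverse event window covers only the first administration, so Dysport Cycle tables report event percentages over unequal time at risk

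*SAP*

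**What the plan says.** SAP 7.7.1 plans 12-week versions of two TEAE tables. The overview counts "only TEAEs occurring any time after first dose of IMP until up to 12 weeks after first IMP treatment administration". For the SOC/PT summary, "this table will be provided including only TEAEs occurring up to 12 weeks after first IMP treatment administration". The reason is given with the overview: "In view of the anticipated difference in duration of the Dysport and placebo treatment cycles".

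These tables belong to the double-blind placebo-controlled (DBPC) cycle. Under SAP 7.1, "During analysis of the DBPC (DBPC cycle), data will be displayed using the following treatment group labels, in the order presented": placebo, 600 U, 800 U and All Dysport.

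Repeat treatment is shown by Dysport Cycle. An event that starts or worsens after one Dysport dose and "prior to the time of treatment administration of Dysport Cycle X+1, Day 1, the TEAEs will be assigned to Dysport Cycle X". Dysport Cycle 1 has two sources: "Data from subjects who received Dysport as their first study treatment on Day 1" and "Data from subjects who received a Dysport treatment after having initially received placebo as their first study treatment on Day 1". SAP 7.1 sets percentage denominators as numbers of subjects in the population for the cycle concerned. Exposure in weeks is summarised separately in SAP 7.5. Section 7.7.1 describes neither a 12-week version per Dysport Cycle nor a rate per unit of exposure.

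On follow-up, the protocol synopsis (End of Study Visit) states that "a minimum of 12 weeks of follow-up is required after each IMP administration".

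**The concern.** The SAP identifies a problem of unequal time at risk and solves it for one administration. The same problem arises in every Dysport Cycle, where the cycle ends when the subject is retreated or leaves the study.

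Cycle length is itself an efficacy outcome. Time between treatments is one of the duration-of-effect endpoints, and SAP 7.6.6.4 plans log-rank comparisons of it between treatment groups, in the Dysport Cycles as well as the DBPC Cycle. Protocol 1.5 expects more efficacy from 800 U. If one dose lasts longer, its whole-cycle percentages include more background events, and Protocol 1.7 notes that this population is already prone to urinary tract infection. Later cycles also have less study time left to run.

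Safety of the two doses is a stated objective, and SAP 7.1 makes evaluation over repeated Dysport treatments part of the analysis strategy. Readers will set these percentages side by side even though nothing is tested.

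**Working it through.** **Reproducing the plan's own timing.** Last permitted retreatment at Week 104, plus 12 weeks of follow-up: 104 + 12 = 116 weeks. This matches the maximum participation in Protocol 3.4.

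**Step 1: coverage of the 12-week window.** Planned allocation (SAP 2.2) is 110 to 600 U, 110 to 800 U, and 55 + 55 placebo starters who move to 600 U or 800 U.
- First Dysport exposures per dose: up to 110 + 55 = 165.
- Inside the window: 110/165 = 67%.
- Outside it: 55/165 = 33%, plus every retreatment in both doses.

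**Step 2: how far cycle length can vary.** Inputs are the minimum interval of 12 weeks between doses and the nominal end at Week 104. The longest possible Dysport Cycle k, in nominal weeks, is:
- Dysport starters, 104 − 12(k − 1): 104, 92, 80 and 68 for k = 1 to 4.
- Placebo starters, 104 − 12k: 92, 80, 68 and 56 for k = 1 to 4.

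The shortest cycle in a subject who completes follow-up is about 12 weeks, for example after retreatment at Week 104. So length is not fixed, the maximum falls with cycle number, and Dysport Cycle 1 mixes two maxima. That mix is planned as 110 to 55 in both doses, so it does not separate the doses by itself. A dose artefact needs one dose to have longer cycles.

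**Step 3: size of the artefact.** Assume a constant event rate that is the same in both groups compared. With p12 the proportion with an event in 12 weeks, the proportion over a cycle of L weeks is

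I(L) = 1 − (1 − p12)^(L/12).

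Example with p12 = 10%: I(36) = 1 − 0.9³ = 27.1%; I(48) = 1 − 0.9⁴ = 34.4%; difference 7.3 points with no true difference in rate.

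| p12 | 36 vs 40 weeks | 36 vs 48 weeks | 24 vs 52 weeks |
|---|---|---|---|
| 5% | 1.5 points | 4.3 points | 10.2 points |
| 10% | 2.5 points | 7.3 points | 17.7 points |
| 20% | 3.7 points | 10.2 points | 26.0 points |
| 30% | 3.8 points | 10.3 points | 27.7 points |

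Both p12 and the cycle lengths are assumptions, because the documents give neither.

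**Step 4: with a window in every cycle.** L = 12 for everyone, so I(12) = p12 in each group and the artefact is 0.

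**Step 5: the opposite case.** If all events fall within 12 weeks of injection, I(L) = p12 for any L of 12 or more, and the whole-cycle tables carry no artefact either.

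**Step 6: feasibility.** Retreatment requires more than 84 days since the previous dose (SAP 2.2), so the next dose does not cut a 12-week window short. The follow-up is already required after each administration.

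**The case against.** The main dose comparison is already protected. The DBPC groups include both doses, so the 12-week tables give a randomised, equal-window display of 600 U against 800 U, 110 versus 110 planned. A reader might infer that the doses are compared only over whole cycles of unequal length, or that a longer-acting dose will look more toxic. The documents do not support this for the first treatment, and they do not say that cycle lengths differ by dose. This part of the objection stands in full.

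Safety is descriptive and the protocol plans no inference on it. This also stands: no test or decision rule uses the Dysport Cycle percentages.

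The displays closest to drug toxicity are partly protected. IMP-related TEAEs are tabulated by cycle, and adverse events of special interest are excluded when their timing after the last treatment does not fit the mechanism. This limits the concern mainly to all-cause TEAEs.

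Cycle length is also visible elsewhere, through Kaplan-Meier summaries of time between treatments and the exposure tables. That tells the reader that durations differ but does not correct the percentages.

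A reader might also infer that repeat treatment will appear progressively safer from cycle to cycle. The figures in Step 2 are maxima only. The tables are organised by cycle number, and each number can mix early and late retreatments, so the actual pattern cannot be predicted.

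Finally, the table shells are a separate document and the appendices are not in the public copy. A per-cycle window could be specified there, but the SAP text does not require one.

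**Conclusion.** The gap is real but narrow. The fixed window works for the first administration and should be credited for that. It does not reach placebo starters' first Dysport dose (55 planned per dose) or any retreatment. For these, SAP 7.7.1 describes only whole-cycle percentages of subjects, without a window or exposure adjustment.

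Descriptive differences between cycles, and between doses within Dysport Cycles, therefore mix event rate with time at risk. Under a constant rate the artefact runs from 1.5 points (p12 of 5%, 36 versus 40 weeks) to 27.7 points (p12 of 30%, 24 versus 52 weeks). It approaches zero for events that cluster soon after injection. These figures rest on assumed rates and cycle lengths, and on a common cycle length within each group compared. No efficacy conclusion or tested hypothesis is affected. The change is worth making as a low-cost improvement to the repeat-dose safety displays.

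**What to change.** In SAP 7.7.1, also produce the TEAE overview and the SOC/PT table for each Dysport Cycle, counting events from that cycle's administration up to 12 weeks after it, by 600 U, 800 U and All Dysport. Name these as the main descriptive display across doses and cycles. Keep the whole-cycle tables, because they capture every event, including late ones.

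Add a footnote that the window equalises time but not populations: later cycles contain only subjects who stayed in the study, asked for retreatment and met the criteria. Align the table shells with the new text.

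The cost is a few additional tables from existing programs with a date filter. No new data or visits are needed. Subjects who withdraw within 12 weeks of a dose will still have shorter observation.

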7.7.2 Laboratory Evaluations

Clinical laboratory data from the central laboratory (haematology, biochemistry and urinalysis, and urine culture and sensitivity) will be listed in Standard International (SI) units. Any unscheduled laboratory assessments will be included in the listings. For post-baseline, only data from scheduled visits will be included in the summary tables.

Haematology parameters:

- Red blood cell count
- Haemoglobin
- Haematocrit
- Mean corpuscular volume
- Mean corpuscular hemoglobin
- Mean corpuscular hemoglobin concentration
- White blood cell count with differential (neutrophils, lymphocytes, monocytes, eosinophils, basophils, and others)
- Platelet count.

Serum Chemistry parameters:

Statistical Analysis Plan

Version:Final v2.0

September-2018

Ipsen Protocol No. D-FR-52120-222

000000146259

Date of Issue: 21-

Covance Study ID:

- Urea, creatinine, total bilirubin, conjugated bilirubin
- Chloride, bicarbonate, sodium, potassium, calcium, inorganic phosphate
- Alkaline phosphatase, aspartate aminotransferase, alanine aminotransferase, gamma glutamyl transferase
- Albumin, total protein, total cholesterol, triglycerides, fasting glucose.

Urinalysis parameters:

- pH, protein, ketones, bilirubin, blood, urobilinogen, nitrites, leukocytes, glucose and specific gravity

Laboratory results will be classified as low, normal, or high at each visit according to the laboratory supplied reference ranges. Abnormal values will be flagged (High [H], Low [L]) in the data listings. A list of clinically significant abnormal values will be presented by treatment group and subject ID.

Descriptive statistics will be presented for actual values and changes from study baseline at each scheduled assessment by treatment group.

The number and percentage of subjects will be summarised for clinical significance of each abnormal value.

For each scheduled post-baseline assessment visit, shift from study baseline tables of the number and percentage of subjects with low, normal or high values will be presented.

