5 STUDY PROCEDURES

5.1 Study Schedule

The schedule of procedures and assessments during the study is summarised in [Table 4](#) for Screening and Treatment 1 follow-up and in [Table 5](#) for retreatment assessment and follow-up.

Table 4 Study Procedures and Assessments for First Treatment and Follow-Up Until Retreatment or End Of Study

	Screening		Treatment	Post-Treatment 1 Follow-up						End of Study/ Withdrawal
	Screening Visit 1	Screening Visit 2 [h][p]	Treatment Visit (Day 1) [h]	Week 1 Visit (Day 8)	Week 2 Visit (Day 15)	Week 4 Visit (Day 29)	Week 6 Visit (Day 43)	Week 12 Visit (Day 85)	Routine Visit every 12 weeks (84 days) until retreatment occurs	End of Study Visit (Week 104 to Week 116) [o]
	Clinic	Clinic	Clinic	Telepho ne [m]	Clinic	Telepho ne [m]	Clinic	Clinic	Telephone [m]	Clinic
Visit window (days)	-30 to -1 [p]		Within 14 days of Screening Visit 2 [h]	±3 days	±3 days	±3 days	±3 days	±7 days	±14 days	±14 days
Informed consent	X									
Demographic data	X									
Medical/surgical/NDO history	X									
Prior medications and therapies	X									
Inclusion/exclusion criteria	X	X	X							
Concomitant medications and therapies	X	X	X	X	X	X	X	X	X	X
Prior and concomitant treatments for NDO [a]	X	X	X	X	X	X	X	X	X	X
Adverse events	X	X	X	X	X	X	X	X	X	X
Physical examination (symptom-based)	X						X			X
Vital signs	X [f]		X [l]		X		X	X		X
Urinary tract ultrasound	X [g]									
Urine pregnancy test [b]	X		X							
Laboratory urinalysis/microscopy [c]	X						X	X		X
Urine culture [c]	X						X			
Dispense antibiotics		X [i]					X [n]			
Haematology and serum chemistry	X						X			X
Anti BTX-A antibodies	X						X			X
Dispense bladder diary & training [d]	X									
Bladder diary review		X [j]			X [j]		X [j]	X [j]	X [j]	X [j]
I-QoL and EQ-5D-5L			X				X	X		X
mPGI-I [e]					X		X	X	X	X
Urodynamics (filling cystometry)		X [k]					X			
Randomisation			X							
IMP administration			X							

BTX-A=botulinum toxin type A; EOS=End of Study; EQ-5D-5L=EuroQoL 5-dimension 5-level; IMP=investigational medicinal product; I-QoL=incontinence quality of life; mPGI-I=modified patient global impression - improvement; NDO=neurogenic detrusor overactivity.

-
- a Concomitant treatments for NDO (e.g. anticholinergics, beta-3 agonists, clean intermittent catheterisation rate) should remain stable during the first 12 weeks after Treatment 1 (preferably for the entire duration of the study).

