- b Pregnancy test to be performed only in females of childbearing potential. Must be performed prior to randomisation on the day of treatment.
- c Laboratory urinalysis/microscopy and urine culture to be performed at any follow-up visit if there is a suspicion of urinary tract infection based on subject symptoms. See [Section 6.4.1.3](#) for further details.
- d Bladder diary device to be returned when subject completes study (e.g. in the event of screen failure, EOS Visit, Early Withdrawal Visit, etc.)
- e mPGI-I will be completed on the electronic bladder diary device and should be completed at home prior to the visit.
- f Body weight and height will be measured at Screening Visit 1 only.
- g Urinary tract ultrasound is only required if no adequate documented urinary tract ultrasound is available in the 6 months prior to Screening (see inclusion criterion #11).
- h Treatment Visit should occur within 14 days of Screening Visit 2 (where a UTI occurs and impacts the ability to perform IMP administration the time to the Treatment Visit can be extended until the UTI is resolved). Both visits may be performed on the same day, as long as all Screening Visit 2 procedures are performed prior to the Treatment Visit procedures and antibiotics were commenced 3 or more days prior to treatment (see [Section 6.4.1.2](#)).
- i Adapted antibiotics based on screening urine culture sensitivities must be provided to cover both the urodynamic procedure (at least 2-day course starting on the day of the urodynamics) and to cover the treatment administration **CCCCI** See [Section 6.4.1.2](#) for further details.
- j Site should check if bladder diary has been commenced at least 8 days prior to visit. If not commenced then site should contact subject to remind subject (and/or caregiver) to commence collecting bladder diary data. Electronic bladder diary data may be reviewed by the site prior to the visit (recommended, to check if bladder diary is fully completed).
- k Screening urodynamics should only be performed if the subject is eligible based on a valid screening 7-day bladder diary.
- l At the Treatment Visit, vital signs will be recorded before and at least 30 minutes after treatment administration. In addition, blood pressure and heart rate will be monitored during the entire treatment procedure in subjects with spinal cord injury with vertebral lesions above the T6 level.

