8.2.7 Other Laboratory Safety Tests

Other laboratory safety tests may be performed at the discretion of the investigator to ensure the safety of the subjects.

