8.2.8 Blood Volume to be Collected During the Study

The blood volume collected during the 24-month course of the study depends on the number of treatment cycles received. Assuming 3 mL of blood sampled for each haematology test, 4 mL of blood sampled for each biochemistry test (for serum chemistry), and 12 mL of blood sampled for each antibody test:

- A subject who receives a single study treatment will provide 57 mL of blood
- For each additional treatment cycle, the subject will provide a further 26 mL of blood.

A subject who receives 3 study treatments will therefore provide 109 mL of blood during their study participation.

The maximum amount of blood collected at a single visit is 19 mL (for visits at which samples are collected for all blood tests).

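### Post-baseline laboratory tables use scheduled visits only, so a new abnormality first seen on an unscheduled blood test is missing from the by-arm abnormality counts and shifts

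*SAP*

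**What the plan says.** SAP 7.7.2 separates listings from tables. For the listings it states: "Any unscheduled laboratory assessments will be included in the listings". For the tables it states: "For post-baseline, only data from scheduled visits will be included in the summary tables". Two of the planned tables are the ones a safety reader would use to compare arms:

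- Abnormal values by clinical significance: "The number and percentage of subjects will be summarised for clinical significance of each abnormal value".
- Shifts, which are explicitly by visit: "For each scheduled post-baseline assessment visit, shift from study baseline tables of the number and percentage of subjects with low, normal or high values".

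The same section flags high and low values in the listings and provides a separate list of clinically significant values by treatment group and subject. It describes no summary of the worst, or of any, post-baseline value.

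In Protocol Table 4 (Section 5.1), the row "Haematology and serum chemistry" is marked after Treatment 1 only at Week 6 and at EOS/Withdrawal. Table 5 adds the Retreatment Assessment Visit and the Week 6 visit after each retreatment.

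Outside that schedule the protocol allows or requires further tests. Section 8.2.7 states: "Other laboratory safety tests may be performed at the discretion of the investigator to ensure the safety of the subjects". Section 8.2 requires clinically relevant abnormal tests to be repeated until they settle or are explained. Footnote c of Table 4 adds: "Laboratory urinalysis/microscopy and urine culture to be performed at any follow-up visit if there is a suspicion of urinary tract infection based on subject symptoms".

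**The concern.** Unscheduled tests are often taken because someone suspected a problem. If the interval between scheduled blood draws is long, a new abnormality may well be found first on such a test. Under the SAP rule that subject is absent from the laboratory abnormality count and from the shift table, unless a scheduled visit happens to catch the abnormality too. The by-arm laboratory percentages would then describe what was seen at a few planned visits, not how many subjects ever had an abnormal value.

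Other parts of the SAP are less restrictive. Section 6.1 lets efficacy analyses use an unscheduled visit when the nominal visit is missing. Section 7.7.3 counts seroconversion from any positive post-treatment sample. Section 7.7.1 counts subjects with at least one event per cycle, and adds a 12-week version because placebo and Dysport cycles are expected to differ in length. The laboratory data have no equivalent.

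**Working it through.** **1. Confirm the blood schedule from the protocol's own volumes (Section 8.2.8).**

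Inputs per test: haematology 3 mL, chemistry 4 mL, antibody test 12 mL.

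- Full draw: 3 + 4 + 12 = 19 mL, which matches the stated maximum per visit.
- One treatment, with draws at Screening Visit 1, Week 6 and EOS: 3 × 19 = 57 mL. The protocol states: "A subject who receives a single study treatment will provide 57 mL of blood". This reproduces.
- Each further cycle, with the Retreatment Assessment Visit (19 mL) and Week 6 without antibodies (3 + 4 = 7 mL): 19 + 7 = 26 mL. This matches the stated 26 mL.
- Three treatments: 57 + 2 × 26 = 109 mL. This matches the stated 109 mL.

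One more haematology and chemistry draw, say at Week 12, would give 57 + 7 = 64 mL. The stated 57 mL therefore leaves no room for another scheduled draw. Table 13 agrees: Week 12 has urinalysis but no blood sample. The later 12-weekly visits are by telephone.

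**2. Length of the interval for a completer who is never retreated (EOS at Week 104, Section 5.2.7).**

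- 104 − 6 = 98 weeks; 98/104 = 94% of follow-up.
- With the visit windows (Week 6 at Day 43 ± 3; EOS at Day 729 ± 14): shortest 715 − 46 = 669 days, longest 743 − 40 = 703 days.

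This is calendar time without a scheduled blood test. It is not a proportion of results lost.

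**3. Follow each kind of result through the SAP.**

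| Result | Listing | AE tables | Laboratory counts and shifts |
|---|---|---|---|
| New abnormal blood value, first seen on an unscheduled test | Yes | Only if it meets the AE criteria (Protocol 8.1.2.4) | No |
| Repeat of an abnormal scheduled result | Yes | As above | Subject usually already counted; further worsening may be missed |
| Symptom-driven urine sample at a scheduled visit | Yes | UTI rows if reported as a UTI | SAP does not say how it is classified |
| Bloods at a Retreatment Assessment Visit held as an unscheduled visit (Table 5, footnote d) | Yes | As above | SAP does not say; a literal reading could exclude them |

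The first row is the gap. The last row is an ambiguity about samples that the protocol itself requires.

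**The case against.** The strongest reply is that clinically important results already reach by-arm tables. Protocol 8.1.2.4 calls for a laboratory abnormality to be reported as an AE if the investigator considers it clinically significant, if it needs intervention or diagnostic evaluation, or if it changes the administration of study drug. SAP 7.7.1 tabulates those events per cycle and to 12 weeks, with no scheduled-visit limit. This stands. For clinically significant values the added count would overlap heavily with the AE tables, and what is left uncounted is mainly out-of-range values that did not meet the AE criteria. The overlap is not complete, because AE tables do not show low/normal/high shifts.

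It is also fair that scheduled-only tables give both arms the same planned assessments, that safety is descriptive with no inferential comparison planned, and that table layouts sit in a separate shell document that was not available. The first two are reasons to keep the by-visit tables. The third cannot override a rule stated in the SAP text.

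A reader might infer three stronger things that the documents do not support.

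- That concern-driven and repeat tests never count. A repeat of an abnormal scheduled result usually loses no subject, and a symptom-driven sample taken at a scheduled visit may count as scheduled data.
- That the loss is larger on Dysport, because long responders go longer without bloods. This is conceivable, but no figure in either document gives the number of unscheduled tests or their distribution by arm.
- That 94% applies widely. It applies only to blood tests in completers who are never retreated. Urinalysis is also scheduled at Week 12, an early withdrawal should have bloods at the Withdrawal Visit, and each retreatment adds two scheduled draws. Renal impairment does not strengthen the inference: Protocol 1.1.1 attributes it to raised bladder pressure from the disease and does not present it as a drug risk.

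**Conclusion.** The point holds as a reporting gap, and it merits a cheap improvement. The SAP rule is explicit, and the blood-volume arithmetic independently confirms that a never-retreated completer has no scheduled haematology or chemistry for 98 weeks. A new abnormality first seen on an unscheduled blood test in that time is listed, and is tabulated as an AE if it qualifies, but it is left out of the laboratory abnormality counts and shifts. No data are lost and the efficacy conclusions are unaffected.

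The size of the understatement is unknown, because it depends on how many unscheduled tests are done. Any difference between arms is unknown for the same reason. The conclusion assumes that the clinical-significance count falls under the scheduled-only sentence, as its wording implies, and that no worst-value table is hidden in the separate shells. Protocol 8.2.7 does not say which laboratory runs discretionary tests. A result from a local laboratory would lie outside the central laboratory data that SAP 7.7.2 handles, so the change below would not recover it.

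**What to change.** In SAP 7.7.2:

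1. Keep scheduled-visit data for the by-visit descriptive statistics and by-visit shifts.
2. For the DBPC Cycle and for each Dysport Cycle, add (a) a shift from study baseline to the worst post-baseline value and (b) the number and percentage of subjects with any abnormal, and with any clinically significant, haematology or chemistry value. Base both on all central laboratory results, scheduled and unscheduled.
3. Give a DBPC version limited to the first 12 weeks, as SAP 7.7.1 already does for treatment-emergent AEs.
4. State that bloods from the Retreatment Assessment Visit count even when that visit is unscheduled, and assign them to the cycle before the retreatment.
5. Urinalysis can stay scheduled-only or be shown separately. Samples triggered by a suspected UTI would largely restate the UTI rows of the AE tables, and Protocol 8.2.3 already expects frequent urinalysis abnormalities in this population.

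The cost is a short SAP edit and a few tables from results that will be listed anyway; no new data collection is needed. The drawback is that subjects tested more often, or followed in longer cycles, have more chances of an abnormal value. The 12-week version removes most of the effect of cycle length but not that of testing frequency, so a footnote should say so.
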